#### 7.3.4.1 Hematologic Toxicity

Cetuximab will not be dose reduced or held for hematologic adverse events, such as neutropenia, neutropenic fever, or thrombocytopenia.

#### 7.3.4.2 Non-Hematologic Toxicity

##### 7.3.4.3 Pulmonary Toxicity

Interstitial lung disease (ILD), including 1 fatality, occurred in 4 of 1570 (<0.5%) patients receiving Cetuximab in clinical trials. Interrupt Cetuximab for acute onset or worsening of pulmonary symptoms. Permanently discontinue Cetuximab for confirmed ILD.

##### 7.3.4.4 Dermatologic Toxicity

Dermatologic toxicities, including acneform rash, skin drying and fissuring, paronychial inflammation, infectious sequelae (for example *S. aureus* sepsis, abscess formation, cellulitis, blepharitis, conjunctivitis, keratitis, cheilitis), and hypertrichosis occurred in patients receiving Cetuximab therapy. Acneform rash occurred in 76–88% of 1373 patients receiving Cetuximab in clinical trials. Severe acneform rash occurred in 1–17% of patients. Acneform rash usually developed within the first two weeks of therapy and resolved in a majority of the patients after cessation of treatment, although in nearly half, the event continued beyond 28 days. Monitor patients receiving Cetuximab for dermatologic toxicities and infectious sequelae. Instruct patients to limit sun exposure during Cetuximab therapy.

#### **7.3.4.5 Hypomagnesemia and Electrolyte Abnormalities**

In patients evaluated during clinical trials, hypomagnesemia occurred in 55% of patients (199/365) receiving Cetuximab and was severe (NCI CTCAE Grades 3 and 4) in 6–17%. The onset of hypomagnesemia and accompanying electrolyte abnormalities occurred days to months after initiation of Cetuximab. Periodically monitor patients for hypomagnesemia, hypocalcemia, and hypokalemia, during and for at least 8 weeks following the completion of Cetuximab. Replete electrolytes as necessary.

#### **7.4.3 Concomitant Medications**

There are no concomitant medications that are contraindicated with cetuximab.

#### **7.3.6 Supportive Care Guidelines**

##### **7.3.6.1 Rash management**

Patients developing dermatologic adverse events while receiving cetuximab should be monitored for the development of inflammatory or infectious sequelae, and appropriate treatment of these symptoms initiated. Below are suggestions for managing cetuximab induced rash:

**Antibiotics:** The benefit of routine antibiotics in uncomplicated (uninfected) rash is unclear. Some clinicians have used oral minocycline (Minocin), mupirocin (Bactroban), or topical clindamycin (Cleocin). Rash complicated by cellulitis should be treated with appropriate antibiotics based on clinical judgment or microbial sensitivity analysis.

**Antihistamines:** Benadryl or Atarax may be helpful to control itching.

**Topical Steroids:** The benefit of topical steroids is unclear. Topical hydrocortisone cream will be provided for pruritis not relieved with antihistamine use.

**Retinoids:** No data to support use. Use is not advised. They will not be used prophylactically.

**Benzoyl peroxide:** Should NOT be used as it may aggravate rash.

**Makeup:** Rash can be covered with makeup; this should not make it worse (use a dermatologist-approved cover-up, e.g., Dermablend, or any other type of foundation). Remove makeup with a skin-friendly liquid cleanser, e.g., Neutrogena, Dove, or Ivory Skin Cleansing Liqui-Gel.

**Moisturizers:** Use emollients to prevent and alleviate the skin dryness, e.g., Neutrogena Norwegian Formula Hand Cream or Vaseline Intensive Care Advanced Healing Lotion.

**Sunlight:** It is recommended that patients wear sunscreen and hats and limit sun exposure while receiving cetuximab as sunlight can exacerbate any skin reactions that may occur.

**Over-the-counter medications:** Over-the-counter acne vulgaris medications (e.g., benzoyl peroxide) are not advised. This rash is not like acne vulgaris and these treatments could make it worse.

### 7.3.6 Adherence/Compliance

Patients will receive weekly cetuximab per their medical oncologist. They should adhere to their oncologist's recommendations (based on the protocol) regarding administration of cetuximab. Failure to do so may result in removal from the study.

## 8. Toxicity Monitoring and Adverse Event Reporting

All patients who receive one dose of protocol therapy will be evaluable for assessment of toxicity. Prior to each cycle the treating physician will fully assess the patient's condition with respect to possible treatment related toxicities. All adverse events, whether observed by the physician or reported by the patient, occurring during the active portion of therapy, or up to 30 days after the last dose of treatment will be graded by a numerical score according to the NCI's Common Terminology Criteria for Adverse Events (CTCAE), Version 4.0 (<http://ctep.cancer.gov/reporting/ctc.html>) and recorded in the patient's medical record. For the purposes of reporting laboratory abnormalities, only Grade 3-4 adverse events will be recorded on the adverse event CRF pages. Grade 1-2 laboratory abnormalities will not be recorded on the adverse event CRF pages. Information entered on the adverse event CRF pages will include:

- Specific type and duration of reaction (i.e., start and stop dates, resolution).
- Severity/grade.
- Relationship to study drug (causality, attribution).
- Management of the event, if treated with medication and other actions taken to alleviate the clinical event.
- Whether or not it was considered a SAE.

A preexisting condition is one that is present at the start of the study. A preexisting condition will be recorded as an adverse event if the frequency, intensity, or the character of the condition worsens during the study period.

### 8.1 Adverse Event Reporting Requirements

An adverse experience is defined as any unintended or abnormal clinical observation that is not of benefit to the patient. Either the condition was not present prior to exposure to the study therapy, or it has worsened in intensity or frequency following exposure to the study therapy.

All “unexpected” (defined below) and/or “serious” (defined below) adverse events occurring during the active portion of therapy, or up to 30 days after the last dose of treatment, will be reported to the OHRS at [contact] or [contact]. Events will be promptly reported, in writing, to the local IRB in accordance with IRB policy. If a death occurs the IRB will be notified within 24-hours of initial receipt of information. All other SAEs must be reported to the IRB within three to ten days of initial receipt of information. Written follow-up reports are required when additional information is needed to fully characterize the event. Copies of each report sent to the IRB will be kept in the study regulatory file.

In addition to reporting to the local IRB, reporting to external bodies such as industry and/or the FDA may be necessary. The Oncology group affiliates site will report all SAEs to the OHRS will be responsible for forwarding SAE reports to the IRB and FDA.

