### **5.6 Study Enrollment Procedures**

A copy of the institution's IRB-approved informed consent document and written justification for any changes made to the informed consent for this protocol must be on file at the Rutgers Cancer Institute of New Jersey's Office of Human Research Services (OHRs) before any participating institution may enter patients. The CINJOG institution consent form must be reviewed and approved by OHRs Regulatory Affairs and all documents must be received (i.e., IRB approved documentation, IRB approved consent form, etc.).

To register eligible patients on this study, each site will contact OHRs. Contact information will be provided at the time of site activation. The signed and dated eligibility checklist, completed signature page of the consent form and additional source documents if requested by OHRs will need to be provided. Once OHRs verifies eligibility, a unique patient study number will be issued. The patient will not be identified by name. This is the point that the patient is considered on study. Patients must not start protocol treatment prior to registration.

If a patient does not receive any protocol therapy, baseline data will be collected and submitted on the pre-study and follow-up electronic case report forms (eCRF). The reason for not starting protocol therapy will be documented in the "follow-up eCRF". Case report form completion instructions and training will be provided to each participating institution prior to study activation at the participating institution.

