#### **8.3 Definition of Related**

There is a reasonable possibility that the drug caused the adverse experience. That is, the event is judged by the investigator to be possibly, probably or definitely related to the treatment.

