## **11.2 Tissue to be collected**

All patients must have a diagnosis of squamous cell carcinoma (SCC) of skin prior to entering into this protocol. This diagnosis is typically achieved by a biopsy from either the primary site or FNA from a neck lymph node. However, the scant amount of tissue obtainable from an FNA would not be adequate for the molecular biology aspect of this protocol, which include

1. Providing tissue to the pathology department so that they are able to confirm diagnosis of SCC in the tissue retrieved, which then will be sent to FoundationOne™ for DNA sequencing and analysis of genetic mutations.
2. Providing frozen tumor to the Cancer Institute Functional Genomics Facility for RNA sequencing
3. Providing frozen tumor and skin tissue to be used in Western Blot analysis.
4. Providing FFPE tumor and skin tissue for use in IHC analysis.

Thus, all patients on the protocol, prior to neoadjuvant cetuximab, will have an incisional/core biopsy from the primary site and a skin punch biopsy even though they already have a diagnosis of SCC. Incisional biopsy is favored over other types (core biopsy) for this biopsy because incisional biopsy has the best chance of supplying an adequate tumor sample.

After neoadjuvant cetuximab, additional tissue will be obtained at surgery or if the patient is not a candidate for surgery, biopsy will be obtained prior to treatment with XRT or with further systemic therapy. This tissue will only be used for RNA sequencing (and not sent to FoundationOne™ for DNA analysis), and thus a core biopsy may be employed here instead of incisional biopsy. A skin punch skin biopsy will also be performed after neoadjuvant cetuximab, preferably from a similar location as the first skin biopsy i.e. obtain two skin biopsies of neck and neck or right upper chest and right upper chest. If there is a locoregional/distant recurrence or persistence, a third incisional biopsy of locoregional/distant disease if possible and again paraffin-embedded sample will be sent to FoundationOne™ for analysis and fresh tissue may be obtained for RNA sequencing.

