### **16.2 Potential Risks**

Potential risks to the patient secondary to cetuximab include the potential for hypersensitivity reaction, rash, hypomagnesemia, and pulmonary complications. These will be monitored as detailed in Sections 7.3.3. In terms of the individual's cancer, there is a risk of treatment not being effective. Furthermore, if the drug is not effective, there is the possibility of disease progression.

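### Adverse event collection opens with study therapy and closes 30 days after the last dose, so research-biopsy complications outside that window carry no recording or reporting duty

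*Combined protocol and SAP*

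**What the plan says.** **Definition.** Section 8.1 counts a clinical observation as an adverse experience on one of two conditions. The first is: "Either the condition was not present prior to exposure to the study therapy". The second is a worsening after treatment began.

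**Window.** Section 8 says that events "occurring during the active portion of therapy, or up to 30 days after the last dose of treatment will be graded" and entered in the record. Section 8.1 sets the same limits for expedited reporting of unexpected and/or serious events to OHRS: "adverse events occurring during the active portion of therapy, or up to 30 days after the last dose of treatment, will be reported to the" office concerned. Under section 8, a patient becomes evaluable for toxicity after one dose.

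**Attribution.** Section 8.3 defines related as: "There is a reasonable possibility that the drug caused the adverse experience". The causality item that section 8 lists for the AE CRF refers to the study drug.

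**Research procedures.** Section 11.2 says that all patients, before the first dose, "will have an incisional/core biopsy from the primary site and a skin punch biopsy even though they already have a diagnosis of SCC". Section 5.1.3 makes agreement to pre- and post-treatment biopsies an entry condition, and section 17 calls the pretreatment biopsies mandatory. The section 6 schedule allows tumor and skin biopsies up to 30 days before treatment. It schedules them again around surgery or radiotherapy with no fixed day, and again within 30 days of relapse. Section 11.2 asks for the relapse tumor biopsy only where it can be done.

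**Patients who never start.** Section 5.6: "If a patient does not receive any protocol therapy, baseline data will be collected", and the reason for not starting is entered on the follow-up eCRF.

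**Risks.** Section 16.2 opens: "Potential risks to the patient secondary to cetuximab include the potential for hypersensitivity reaction". It goes on to other cetuximab toxicities, lack of efficacy and progression. Section 16.5 uses that list for the discussion with the patient.

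**The concern.** The pre-treatment biopsies are done for research, in patients whose cancer is already diagnosed. Section 11.3 gives the skin sample no diagnostic role. These are the first invasive procedures that the protocol imposes, and they take place before the rules for adverse events begin to apply.

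A serious bleed or wound infection could follow such a biopsy and resolve before dose 1, or stop the patient from starting. Nothing in sections 8 to 8.4 then requires it to be graded, entered as an adverse event or sent to OHRS. Safety and feasibility of neoadjuvant cetuximab are co-primary in section 1.1. A trial team would also want to know early if the tissue collection itself causes harm, because any later randomized trial might copy it.

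**Working it through.** The plan gives no figure on this point, so the check compares the collection window with the biopsy schedule.

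**Inputs.** Weekly dosing for 8 weeks (7.2.2); 30-day tail (8, 8.1); biopsies up to 30 days before treatment and a week 9 visit (6); 20 patients (4.1). Assumption: dose 1 on day 1 and no dose delays.

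**Window.**
- Last dose: 1 + 7 × 7 = day 50.
- Window closes: 50 + 30 = day 80.
- Week 9 visit: 1 + 8 × 7 = day 57, which is 80 − 57 = 23 days before closure.
- First 3-month follow-up, if local therapy took place on day 57 (assumption): 57 + 91 = day 148, which is 148 − 80 = 68 days after closure.

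Dose delays would move the last dose and day 80 later. They would not change the gap before dose 1.

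**Complications set against the rules.**

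| Complication | Meets the 8.1 definition? | Inside the window? |
|---|---|---|
| Pre-treatment biopsy; onset before dose 1, no later worsening | No | No |
| Pre-treatment biopsy; dose 1 never given | No (no exposure) | No |
| Pre-treatment biopsy; onset or worsening from dose 1 to day 80 | Yes | Yes |
| Post-treatment biopsy; onset by day 80 | Yes | Yes |
| Post-treatment biopsy; onset after day 80 | Yes | No |
| Relapse biopsy; onset after day 80 | Yes | No |

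The first two rows fail on both the definition and the window. The last two meet the definition and are lost only through the 30-day limit.

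**Number of procedures.** At least one tumor biopsy and one skin punch per patient before dose 1: 2 × 20 = 40. Node biopsies in patients with nodal disease (7.2.1) would add to this. One patient unable to start because of a biopsy would be 1/20 = 5% of planned enrollment.

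**Other places that might close the gap.**
- Footnote 1 of the schedule puts a toxicity assessment in the pre-cetuximab, follow-up and after-failure visits. No recording or reporting rule outside the window is attached to it.
- The section 8 rule on pre-existing conditions captures worsening only.
- Section 5.6 records why a patient did not start. That entry is neither a graded event nor an SAE report.

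**Effect on the primary test.** None. The figures in section 15.2 reproduce (rejection at 5 or more responses in 20 gives type I error 4.32% and power 76.2%), and they do not depend on adverse event rules.

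**The case against.** The other side has several good points, and they set the limits of this one.

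- A reader might infer that biopsy harm is lost entirely. The text does not support that. A complication of the pre-treatment biopsy that appears or worsens after dose 1 meets the definition and falls in the window. So does one from a biopsy around week 9.
- A reader might infer that the relapse biopsy is compulsory. Section 5.1.3 requires agreement only to pre- and post-treatment biopsies, and section 11.2 makes the relapse tumor biopsy conditional. Harm from it is also not excluded by the definition, because it was not present before exposure.
- Section 8.3 might seem to block reporting of procedure-related events. It does not: section 8.1 sends unexpected and/or serious events in the window to OHRS whatever their cause. Relatedness limits only the FDA MedWatch rule. What is missing is a place to attribute an event to the procedure.
- The co-primary safety and feasibility objective concerns cetuximab, while the biopsies serve a secondary molecular objective. No feasibility criterion is defined, so no bias in a feasibility result can be derived. A failure to start is documented under section 5.6.
- A reader might infer that patients are not told of biopsy risks. The consent pages were not available, so only the silence of section 16.2 can be confirmed.
- Local IRB policy, which section 8.1 cites but does not reproduce, may impose duties of its own.

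All of these narrow the point. None supplies an AE or SAE duty in this protocol for a complication that starts before dose 1 and does not worsen, or that prevents dose 1.

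**Conclusion.** The concern holds in a limited form. For at least 40 compulsory research procedures before dose 1, a complication with onset before dose 1 and no later worsening, or one that prevents dose 1, has no stated recording or reporting duty. Later biopsies are covered only for events up to 30 days after the last dose (about day 80 with uninterrupted dosing). Post-treatment or relapse biopsies after that are missed because of the limit. Events inside the window are captured but cannot be attributed to the procedure on the AE CRF as described. Section 16.2, on which the risk discussion relies, names no biopsy risk.

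The number of events that would be lost cannot be estimated, since the documents give no complication rate for these biopsies. The conclusion rests on the text of sections 5.6, 8 to 8.4, 11.2 and 16.2, and on the schedule. The day counts also assume no dose delays and, for the follow-up example, local therapy on day 57. The response analysis and sample size are unaffected. This is an inexpensive improvement to safety reporting that should be made.

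**What to change.** - **Sections 8 and 8.1:** record and report AEs and SAEs attributed to a protocol-specified research biopsy from the first such procedure, and for a stated period after each later one (for example 30 days). Include registered patients who never receive cetuximab. Keep the present window for all other events.
- **Sections 8.1 and 8.3:** extend the definitions of adverse experience and related to cover protocol-mandated procedures as well as study therapy.
- **AE eCRF:** add a field for relationship to the procedure, separate from relationship to drug, so that cetuximab toxicity can still be summarized on its own among treated patients.
- **Section 16.2:** add the risks of the tumor, node and skin biopsies, and check that the consent form agrees.

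The cost is amendment wording, one eCRF field and a few more events to record. No procedure, visit or treatment rule changes.

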#### **Reporting SAEs using commercially available drugs:**

In addition, any unexpected (*not listed in the package insert*) serious adverse events that are associated (definitely, probably or possibly related) with the use of cetuximab must be reported to the FDA within 10 business days using a FDA Form MedWatch 3500 form <http://www.fda.gov/medwatch/safety/3500.pdf> (fax # [name]).

#### **8.2 Definition of Serious Adverse Events (SAEs)**

A serious adverse event (experience) is one occurring at any dose level that results in any of the following outcomes:

- Death
- Life-threatening- immediate risk of death from the reaction.
- Requires inpatient hospitalization or prolongation of existing hospitalization.
- Results in persistent or significant disability/incapacity.
- Results in a congenital anomaly/birth defect.
- Requires intervention to prevent one of the outcomes listed in this definition.

The definition of serious adverse event (experience) also includes *important medical events*. Medical and scientific judgment will be exercised in deciding whether expedited reporting is appropriate in other situations, such as important medical events that may not be immediately life-threatening or result in death or hospitalization but may jeopardize the patient or may require intervention to prevent one of the other outcomes listed in the definition above. These events will usually be considered serious. Examples of such events are intensive treatment in an emergency room or at home for allergic bronchospasm; blood dyscrasias or convulsions that do not result in hospitalization.

#### **8.3 Definition of Related**

There is a reasonable possibility that the drug caused the adverse experience. That is, the event is judged by the investigator to be possibly, probably or definitely related to the treatment.

#### **8.4 Definition of Unexpected**

Any adverse drug experience and/or specificity, that is not included in the current investigator's brochure and/or package insert.

### **9. Treatment Evaluation/Criteria for Response**

For the purposes of this study, the response to neoadjuvant cetuximab is judged by 1) development of cetuximab related folliculitis as below and 2) response at the primary site or involved locoregional lymph nodes by CT using RECIST criteria.

Response and progression will be evaluated in this study using the international criteria proposed by the Response Evaluation Criteria in Solid Tumors (RECIST 1.1) Committee (Eisenhauer et al. 2009)Changes in only the largest diameter (unidimensional measurement) of the tumor lesions are used in the RECIST criteria. Note: Lesions are either measurable or non- measurable using the criteria provided below. The term "evaluable" in reference to measurability will not be used because it does not provide additional meaning or accuracy.

In addition, patients will be evaluated weekly during neoadjuvant cetuximab to assess for grade of rash using CTCAE 4.0 criteria.

#### **9.1 Evaluation of folliculitis**

Folliculitis will be graded weekly following the initiation of neoadjuvant cetuximab per the criteria in section 7.3.3.1

#### **9.2 Evaluation of CT response at primary site**

Measurable lesions are defined as those that can be accurately measured in at least one dimension as >10 mm with spiral CT scan. All tumor measurements must be recorded in millimeters (or decimal fractions of centimeters). As all CT scans in this protocol will be performed using spiral CT, no lesions smaller than 10 mm will be used to assess for response.

Response will be graded per RECIST criteria:

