### 5. Patient Selection Criteria

#### 5.1 Inclusion Criteria

A patient is eligible for enrollment if all of the following inclusion criteria are met.

5.1.1 Patients must have untreated or relapsed SCCS that is considered to be aggressive and locally advanced by the following criteria: tumors 2 cm or more, tumors invading deep tissues such as muscle, cartilage or bone; tumors showing perineural invasion, and/or tumors metastatic to loco-regional lymph nodes. Patients may have had prior surgical interventions or been treated with investigational agents with residual or recurrent disease.

5.1.2 Patients must give informed consent.

- 5.1.3. Patients must agree to pre- and post- treatment biopsies.
- 5.1.4 Patients must have an ECOG performance status  $\leq 2$  (Appendix B).
- 5.1.5 Estimated life expectancy of at least 12 weeks.
- 5.1.6 Negative pregnancy test

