## 6. Study Parameters

Evaluations	Pre-cetuximab	Weekly during neoadjuvant cetuximab	Post-cetuximab (Week 9)	At surgery or prior to RT 	30 days after surgery or XRT	Follow ups every 3 months after surgery or XRT for 2 years	After locoregional or distant failure
History, physical exam and tumor site assessment	X  (within 14 days of treatment)	X 	X 		X 	X 	X 
Photo of tumor and/or rash at head, neck, upper torso put into EMR	X (within 14 days of treatment)	X 	X 				
Incisional/core biopsy of primary tumor and loco-regional lymph nodes if involved	X  (within 30 days of treatment)			X  (any time during this interval)			X (within 30 days of relapse)
Biopsy of skin	X  (within 30 days of treatment)			X  (any time during this interval)			X (within 30 days of relapse)
CBC, differential, platelets	X (within 14 days of treatment)	X			X	X	
Serum Chemistries 	X (within 14 days of treatment)	X	X	X	X	X	
Liver Enzymes 	X (within 14 days of treatment)	X			X	X	
Pregnancy Test 	X (within 14 days of treatment)						

Radiographic Assessments 	X  (within 30 days of treatment)		X 			X	X 
---------------------------------------	---	--	----------------	--	--	---	----------------

\*A +/- 2 day window is allowed for all study assessments indicated on this trial except treatment for which a +/- 1 day window is allowed.

1. To include toxicity assessment, ECOG performance status, weight
2. Includes: Electrolytes, including serum magnesium, potassium, Calcium, BUN, Creatinine, Glucose,
3. Includes: Total and Direct. Bilirubin, AST/ALT, Alkaline Phosphatase, Albumin, Total Protein.
4. Women 18-55 who have not undergone menopause must have urine pregnancy test within 14 days of enrollment.
5. Tumor assessments as indicated by investigator, i.e. PET/CT, CT neck, chest/abdomen and pelvis or MRI of neck as needed to be obtained no more than 1 month prior to cetuximab; then per standard of care, in general, every three months after conclusion of surgery or XRT.
6. Every 7 days
7. Includes evaluation by surgery and radiation oncology for optimal local therapy. Surgery will assess optimal timing of rebiopsy during their evaluation of patient once neoadjuvant therapy is complete.
8. See section 11

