## **15. Statistical Considerations**

### **15.1 Primary Hypothesis**

We hypothesize that the response rate to cetuximab is greater than 10%.

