### **15.2 Sample Size Justification**

Sample size was justified based on the primary hypothesis. We expect the response rate is 30%. With 20 patients, the one-sided Binomial exact test at a significance level 0.05 (actual Type I error = 4.32%) will achieve 76.2% power when true response rate is 30%.

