### **15.4 Outcome Measures**

The primary outcome is the response rate of cetuximab by RECIST criteria in patients with advanced SCCS.

The secondary outcomes include time to progression, time to death of patients with advanced SCCS who receive neoadjuvant cetuximab. Molecular correlates and tumor size will be also obtained.

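### Only CT-measured lesions can count toward the primary response, although the primary site is a skin tumor and entry does not require a lesion that CT can measure.

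*Combined protocol and SAP*

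**What the plan says.** Section 15.4 sets the endpoint: "The primary outcome is the response rate of cetuximab by RECIST criteria in patients with advanced SCCS". Section 7.2.3.1 reads it by comparing a contrast CT after 8 weeks with the pre-treatment CT, over the primary site and neck nodes together. Section 9 judges "response at the primary site or involved locoregional lymph nodes by CT using RECIST criteria" (alongside folliculitis, which does not measure tumor) and says that lesions are classed as measurable or not by the criteria that follow it. Those criteria, in 9.2, refer only to spiral CT. On response, they read "As all CT scans in this protocol will be performed using spiral CT, no lesions smaller than 10 mm will be used to assess for". No clinical definition of a measurable lesion is given.

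Entry under 5.1.1 covers "tumors 2 cm or more, tumors invading deep tissues such as muscle, cartilage or bone", as well as perineural invasion and regional nodes. It does not ask for a lesion measurable on CT.

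The schedule in section 6 has a tumor-site assessment and "Photo of tumor and/or rash at head, neck, upper torso put into EMR" at baseline, every 7 days and at Week 9. Nothing in the documents uses either to measure a target lesion, assign a response category or confirm a complete response. Footnote 5 of the same table lets the investigator use PET/CT, CT or MRI for tumor assessment, which does not fully match the CT-only text of 7.2.3.1 and 9.2.

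**The concern.** A tumor of the skin can be seen and measured directly. The trial already schedules visits at which this could be done, yet the endpoint admits only what CT shows. Two things can follow for a tumor that lies mainly at the surface:

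- CT cannot measure it accurately. Under 9.2 it is then not measurable, and a patient with no other lesion has nothing to score.
- It is measured on CT, but the CT diameter does not follow the change in the visible tumor. The response category may then be wrong in either direction.

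The test turns on a small count. Each patient who cannot be scored, or whose response is missed, costs power. Each non-responder scored as a responder raises the chance of a false positive conclusion above the stated level.

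**Working it through.** **Inputs from the plan.** Null rate: "We hypothesize that the response rate to cetuximab is greater than 10" per cent (15.1). Expected rate: "We expect the response rate is 30" per cent (15.2). Test: "With 20 patients, the one-sided Binomial exact test at a significance level 0.05 (actual Type I error = 4.32%) will achieve 76.2% power" (15.2).

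**Reproducing the plan's figures.** With X ~ Binomial(20, p) and success if X ≥ 5:

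- P(X ≥ 5 | p = 0.10) = 0.0432
- P(X ≥ 5 | p = 0.30) = 0.7625

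Both match 15.2. A cut-off of 4 gives type I error 0.133. A cut-off of 6 gives 0.011 with power 0.584. The implied rule is therefore 5 or more of 20, and the sample-size statement is correct as it stands.

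**Inputs the plan does not give.** The documents state neither the share of patients whose tumor CT cannot measure nor any misreading rate. Section 8 says who is evaluable for toxicity, but nothing says how a patient without a scoreable lesion counts for response. All rates below are assumptions.

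**(a) Patients who cannot be scored.** Suppose m of 20 have no CT-measurable lesion and count as non-responders, unrelated to whether they truly respond. Then power = P(X ≥ 5 | 20 − m, 0.30):

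| m | Patients scored | Power | Type I error |
|---|---|---|---|
| 0 | 20 | 0.762 | 0.043 |
| 1 | 19 | 0.718 | 0.035 |
| 2 | 18 | 0.667 | 0.028 |
| 4 | 16 | 0.550 | 0.017 |

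Excluding these patients instead does not help in the rows shown. With 19, 18 or 16 patients, the smallest cut-off with type I error at or below 0.05 is still 5, so the power is the same.

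**(b) Patients scored wrongly.** Let Se be the probability that CT scores a true responder as a responder, and FP the probability that it scores a non-responder as one. Then observed rate = p × Se + (1 − p) × FP.

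For Se = 0.90 and FP = 0.03:

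- Null: 0.10 × 0.90 + 0.90 × 0.03 = 0.117, and P(X ≥ 5 | 20, 0.117) = 0.076
- Expected: 0.30 × 0.90 + 0.70 × 0.03 = 0.291, and P(X ≥ 5 | 20, 0.291) = 0.735

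Over a range:

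| Responders missed | Non-responders falsely called | Type I error | Power |
|---|---|---|---|
| 10% | 0 | 0.029 | 0.66 |
| 20% | 0 | 0.018 | 0.54 |
| 0 | 2% | 0.078 | 0.80 |
| 0 | 5% | 0.153 | 0.85 |
| 10% | 2% | 0.057 | 0.71 |
| 10% | 3% | 0.076 | 0.73 |
| 10% | 5% | 0.122 | 0.78 |

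When both errors occur they partly offset each other in power. In these combined rows the type I error still lies above the stated 4.32%.

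**The case against.** The best defense is that 9.2 protects itself. It counts only lesions that can be measured accurately on CT, so a surface tumor that CT shows poorly should not become a target lesion. This largely stands. It turns much of the problem from wrong scores into patients with no score, which is why calculation (a) comes first. It does not remove the loss.

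Second, the documents do not say that CT shows thin skin tumors poorly, or how many patients will have mainly superficial disease. Section 1 describes locally advanced or unresectable tumors, and deep or nodal disease suits CT. This also stands: the point is a risk of unknown frequency.

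Third, section 9 cites RECIST 1.1, which might be thought to supply a rule for skin lesions. What that source allows cannot be checked here. In any case section 9 ties measurability to the protocol's own criteria, and those name CT only. Footnote 5 of the schedule widens the imaging choice but adds no clinical measurement.

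Fourth, the exams and photographs do have uses: weekly rash grading, and the Week 9 evaluation for local therapy. What they lack is a role in the response endpoint.

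A reader might also infer that a complete response on CT with tumor still visible is a false responder. That does not follow. The endpoint is the response rate, so such a patient is still a responder if the true shrinkage was at least 30%. The type I error is affected only if true shrinkage was less than that.

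**Conclusion.** The point holds as a gap in how the primary endpoint is measured. For a skin tumor, the plan accepts only CT, does not require a CT-measurable lesion at entry, and leaves unused the direct observation that it already schedules. It should be corrected, but it does not show that the primary result will be biased, and it does not challenge the stated type I error or power as calculated.

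The size rests wholly on assumed rates. If 2 or 4 of 20 patients cannot be scored and count as non-responders, power is 67% or 55% instead of 76.2%. With 10% of responders missed and 3% of non-responders falsely called, power is 73% and type I error 7.6%.

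Two stronger readings are not supported. One applies each misreading rate alone and reports the worse figure for each, giving power of 66% and type I error of 10.0% (null rate 0.10 + 0.90 × 0.03 = 0.127). If both errors occur, the combined figures apply. The other takes the 31% chance of exactly 4 or 5 responders at a true 30% rate (0.130 + 0.179) as the chance that a misread reverses the conclusion. A reversal also needs a misread in the right direction: a missed responder when 4 are counted, or a false one when 5 are counted.

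**What to change.** Amend as follows:

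- **7.2.3.1 and 9.2:** allow visible skin lesions with a longest diameter of at least 10 mm as target lesions, measured clinically at the scheduled baseline and Week 9 exams with a ruler in the photograph.
- **One modality per target lesion:** choose it at baseline and keep it at Week 9, with clinical measurement for surface lesions and CT for deep extension and nodes. State that no lesion is counted twice, so that a tumor with surface and deep parts has a defined measurement.
- **Complete response:** allow it only if no tumor is visible at exam or in the photograph.
- **Section 6, photograph row:** reword so that the tumor is always photographed, wherever it lies, with rash added if present. As worded, a photograph of rash alone would satisfy it, and the body sites named may not include the tumor, because eligibility does not restrict tumor location.
- **Section 6, footnote 5:** reconcile the PET/CT and MRI option with the CT-only wording of 7.2.3.1 and 9.2.
- **15.5:** report CT-only response as a sensitivity analysis.

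The sample size, the cut-off of 5, the type I error and the planned power do not change. The cost is amendment wording and a ruler at visits that already exist. The change has to be in place before a patient starts treatment, because a baseline measurement cannot be recovered later. The downside is that clinical measurement varies between readers and is unblinded in a single-arm trial, which could favor response. The ruler photographs let others check it, and the CT-only analysis shows whether the conclusion depends on it.
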